### Study Timeline

Quarter	Pre-Award	Year 1				Year 2				Year 3				Year 4			
		1	2	3	4	1	2	3	4	1	2	3	4	1	2	3	4
Obtain IRB approval	X																
Hire and train research staff	X	X															
Finalize procedure materials	X	X															
Pre-implementation data collection from key clinic stakeholders (Aim 1)			X	X													
Assessing the implementation of WE CARE (Aim 1)				X	X	X	X	X	X	X	X	X	X	X	X	X	
Accrue study sample to measure empiric estimates (Aim 2)					X	X	X	X	X								
Data collection (Aim 2)					X	X	X	X	X	X	X	X	X	X	X	X	
Qualitative work assessing possible			X	X	X	X	X	X	X								

mechanisms (Aim 3)														
Final quantitative data analysis (Aim 3)												x	x	x
Writing and publication of manuscripts					x	x	x	x	x	x	x	x	x	x

## Adverse Event Criteria and Reporting Procedures

The study PIs, [name], will meet weekly with the core research team to review study data, compliance with data collection and security procedures, data storage processes, any actual breaches of confidentiality, along with any other issues of subject safety. We believe that there is only minimal risk involved with the participants, primarily concerning breach of confidentiality. Each week, the study PIs will review with the research team whether any breaches of confidentiality have occurred along with any instances of non-compliance with the study's protocol. Research staff will be in monthly contact with the study site PI at each clinic to review data and study compliance, and to identify any issues with data or emerging patterns of concern. Adverse events (AEs) will be recorded and assessed by the study team and study PIs, both on an individual basis and in aggregate (to discover any trends which could mean additional risks to subjects). Any AE or group of AEs that together meet the definition of Unanticipated Problem (UP) will be reported as soon as possible and within 2 business days to the BUMC IRB, and 7 business days to the NHLBI. An Unanticipated Problem is defined as any event that meets all three of the following criteria: unexpected, possibly related to the research, and suggests that the research places subjects or others at a greater risk of harm than was previously known or recognized. OHRP Guidance on Reviewing and Reporting Unanticipated Problems Involving Risks to Subjects or Others and Adverse Events; OHRP, HHS; January 15, 2007). Throughout the course of the study, the data and adherence to the processes in place to protect the data and prevent any breach of confidentiality will also be monitored monthly by [name] (study PIs) in consultation with [name] (biostatistician). The study PIs are ultimately responsible for the ethical conduct of the study, data integrity, and overall safety of this study.

## Data Management Methods

**Aim 1. Implement WE CARE in the outpatient pediatric hematology setting.** Focus groups with stakeholders from each clinical site will be conducted at baseline to identify perceived facilitators and barriers to implementation. Once WE CARE is implemented in the two experimental sites, we will gather implementation data from stakeholders every six months. Recordings of the focus groups will be audiotaped and transcribed for analysis as word processing text files suitable for manipulation using the qualitative software program, N-VIVO11. The audio-tapes will be transcribed verbatim; each transcript will then be reviewed by a research assistant for accuracy. Recordings will be destroyed after seven years.

**Aim 2. Obtain population-specific empirical estimates of study parameters to plan a pragmatic large-scale cluster RCT.** Data will be collected from parents primarily from parent-administered surveys at enrollment and at follow-up which will occur one year post-index visit. These surveys will be completed in REDCap\* using a study tablet (e.g., iPad). REDCap (Research Electronic Data Capture) is a research focused, electronic web-based data capture system. REDCap is a data collection tool and allows for storage and management of both surveys and databases. REDCap is a secure storage system and meets HIPAA compliance standards. REDCap software will be used to facilitate parent consent, questionnaires, and forms.

A brief telephone interview will be conducted 3, 6, and 9 months post-enrollment to ascertain unmet needs, and contact and enrollment in community-based resources, and parent report of prescription

refills for penicillin or hydroxyurea. A hair cortisol sample will also be collected from the parent at enrollment and 1-year follow-up. Finally, site research staff will collect data from the electronic health record (EHR) on child health outcomes (i.e., adherence to clinic visits, ED visits, hospitalizations, vaso-occlusive episodes, acute chest syndrome, and infections). Data from the EHR will be collected three times (baseline, 6-months post-enrollment, and 12-months post-enrollment). Recordings will be destroyed after seven years.

***Aim 3. Qualitatively assess possible mechanisms linking SDoH interventions to improved health outcomes.*** The in-depth interviews with parents will be recorded, transcribed verbatim, and checked for accuracy. Spanish transcripts will be translated into English to facilitate interpretation by the research team. Transcripts will be entered into NVIVO11, to facilitate coding and analysis.

## Quality Control Method

For the *medical chart review*, each research assistant will periodically (every six months) review at least five randomly selected visits at his or her own site. Inter-rater reliability will be determined using the kappa statistic. Any discrepancies will be reviewed with the co-PIs present and resolved. For the qualitative interviews and focus groups, one quarter of transcripts will be independently double-coded and compared to ensure comprehensiveness and accuracy of coding. Inter-coder concordance will be calculated. The REDCap database used for parent questionnaires will use branching logic and validation rules in order to diminish opportunities for error. There will be no opportunity for errors transcribing parent questionnaires into the study database, because parents will independently enter questionnaire responses directly into REDCap.

## Data Analysis Plan

***Aim 1. Implement WE CARE in the outpatient pediatric hematology setting.*** To code the data, we will analyze each interview initially according to PARIHS's three core components: (1) evidence: attitudes and beliefs about evidence of the WE CARE system; (2) context: organizational, systemic, and sociopolitical features that promote or hinder implementation of WE CARE; (3) facilitation: attributes of the facilitation that supported or impeded the implementation, and needed adaptations. In general, we will follow the general procedures of grounded theory to identify themes that are unexpected. We will first create an initial set of conceptual categories using the Constant Comparative Method developed by Glaser and Strauss. According to this method, the initial conceptual categories are then applied to new data, and the categories are revised to reflect the addition of the new data. Upon completion of this process and review of all transcripts, we will have then identified a series of categories that reflect participants' experiences with the implementation of WE CARE. Passages referring to the different conceptual categories of the PARIHS model and other areas will be marked and identified by terms that reflect the conceptual category. Marked passages will be compared to enable the identification of similarities and differences across study sites. Issues of reliability and validity will be handled in the following way. First, two members of the study team will jointly examine each transcript to develop a common set of content codes, formulate coding rules and develop the codebook. They will independently code additional transcripts using the codebook; they will then meet after each transcript has been coded to compare their findings and assess the reliability of the coding rules. Discrepancies will be resolved and coding rules modified via discussion among the team. This process will be repeated with all coded transcripts. The goal of this qualitative analysis is to establish a shared, coherent set of codes and coding rules through a process of critical review and consensus building.

Run charts will be used to observe changes in specific measures over weeks or months, due to iterative PDSA cycles. Run charts will observe changes in frequency of distribution of screeners by clinic staff, recorded SDoH assessments within the EHR, and resource sheet dissemination by providers for positive screens.

***Aim 2. Obtain population-specific empirical estimates of study parameters to plan a pragmatic large-scale cluster RCT.*** We will summarize the number of parents contacted, lost to follow-up, refusing participation, and enrolled. We will examine this by gender (e.g., father vs. mother). We will note reasons for refusals. We will determine parents' recruitment and attrition rates and receipt of WE CARE using descriptive statistics. We will also determine the data collection completion rate, including hair cortisol, for each data time point (baseline, 3-, 6-, 9-, and 12-month follow-up) via descriptive statistics. Each outcome and process variable described above will be first transformed into its final composite value/score. We will calculate within-group mean and standard deviation of our SDoH, process, mediator and health utilization and health outcome variables. We will also break down the intervention group into two subgroups differentiated by whether parents enrolled in resources at follow-up, and explore any differences. An intention-to-treat approach will be used to explore differences between the intervention and control groups. We will also report all data disaggregated by gender. Two independent sample t-test and chi-square tests will be used to determine bivariate differences. Mixed effects regression models will be used to estimate the effect size of the intervention on SCA outcomes accounting for baseline differences in sociodemographics, types of SDoH, cumulative needs, receipt of services, and *a priori* determined covariates (i.e. sociodemographic characteristics). To explore potential moderators for the intervention effect at the parent, child and family levels (e.g., gender, race, ethnicity, age, language, household income), we will use Rothman's methodology; specifically, we will conduct stratified analyses for each potential moderator followed by using standard interaction terms in our models. We will also explore mediation of our hypothesized potential mediators between SDoH and the intervention with each SCA health outcome using the approach recommended by MacKinnon, Lockwood, and Williams. We will account for the clustering by study site by calculating the intraclass correlation.

***Aim 3. Qualitatively assess possible mechanisms linking SDoH interventions to improved health outcomes.*** Qualitative interviews will be analyzed using applied thematic analysis methodology, including: 1) increasing familiarity with the data and generating preliminary codes; 2) generating initial codes and coding structures, including data reduction and complication; 3) combining codes into higher-level themes; and 4) refining and defining themes and identifying ways in which themes fit together. *A priori* research questions and probes will serve as the initial draft of the coding structure.

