## Design and Methods

### *Study Design*

#### ***Study 1 (Aim 1): The implementation of a practice-based social determinants of health screening and referral intervention in two pediatric hematology clinics to field test key study logistics and understand the facilitators and barriers to implementation and accelerate its adoption***

Two of our four proposed pediatric hematology clinical sites will be randomized to implement WE CARE as standard of care for SCA patients. At baseline and every six months throughout the study period, the Boston Medical Center-based team (hereafter termed the core research team) will conduct focus

groups with stakeholders (e.g., clinical and administrative staff) at each of the four pediatric hematology clinic sites to better understand the barriers and facilitators to implementation of WE CARE. The site PI at each institution will help us identify staff members. Before beginning each focus group, the Boston Medical Center PIs and members of their research team will meet with clinic stakeholders at their staff meetings and provide an overview of the study. The Boston Medical Center-based team will conduct focus groups with pediatric hematology clinic staff every six months throughout the study period.

***Study 2 (Aim 2): Obtaining population-specific empirical estimates of study parameters to plan a future large-scale cluster RCT of WE CARE for children with SCA***

For this study, we will be conducting a pilot cluster RCT. Two of our four proposed pediatric hematology clinical sites (Boston Children's Hospital, Connecticut Children's Medical Center, Hasbro Children's Hospital (HCH) and Yale-New Haven Children's Hospital) will be randomized to implement WE CARE as standard of care for SCA patients. To assign the sites to either the control or the intervention group, we will first fix the number of sites to each group (i.e. 2 sites per group) and then assign sites to group using the random function for the uniform distribution in SAS 9.4.

***Study 3 (Aim 3): Qualitatively assess possible mechanisms linking SDoH interventions to improved health outcomes, such as increasing a parent's ability to manage their child's disease through medication adherence***

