## Statistical Power and Sample Considerations

We will enroll up to 235 subjects in this study, including up to 60 practice staff and 175 parents of children with SCA.

Because the goal for **Aim 1** is to examine the implementation of WE CARE in the outpatient pediatric hematology clinical setting our sampling will be purposeful. Based on our previous experience, we anticipate up to 15 practice staff per site will participate in focus group discussions.

For **Aim 2**, we are proposing to enroll 35 families from each of the four study sites (2 experimental, 2 control) to field test study logistics, including collecting empiric estimates of study parameters for a larger pragmatic trial. To demonstrate the feasibility of our study design, we use ED visits (primary

outcome) and penicillin adherence as examples. Assuming a 5% error rate, and based on our R00 WE CARE study, we expect a cluster coefficient no larger than 0.01. Based on recent data, we expect at least 80% of children in our control group to have at least one ED visit within our study observation period. We expect that our intervention group will have a much lower proportion, with ≤40% having with one or more ED visits. Our proposed study sample has >90% power to detect differences of at least 25% in the proportion of children with ED visits. In addition, based on estimates from the literature we expect a 9-month medication adherence of 40% and 10% in the intervention and control groups, respectively. Our study will have 90% power to detect differences of at least 20% in penicillin adherence, which is considered clinically significant. Consistent with CONSORT guidelines for pilot studies, we will not use results from this study to determine efficacy, since effects sizes from pilot studies likely overestimate or underestimate the true effect size; rather we will determine empiric estimates from the control group as the basis for power calculations for a future multi-site trial.

For **Aim 3**, in order to explore an array of beliefs and practices regarding family contextual factors that promote or prevent effective SCA management, enrollment will continue until saturation is reached (i.e. more interviews will not generate additional information) in primary research questions. Based on our previous experience, we expect 25-35 parents will be sufficient to reach saturation.

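### Ordinary t-tests and chi-square tests of arms randomised by site (2 vs 2) ignore clustering, and calculating an ICC does not correct them

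*Combined protocol and SAP*

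**What the plan says.** Under Study Design, Study 2 (Aim 2), the unit of randomisation is the clinic: the number per arm is fixed at two, and the four sites are then allocated at random. Statistical Power and Sample Considerations plans 35 families per site and states "we expect a cluster coefficient no larger than 0.01", a value taken from an earlier study of the same intervention. The same section says "we will not use results from this study to determine efficacy".

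The Aim 2 paragraph of the Data Analysis Plan has four relevant statements, in this order:

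- "An intention-to-treat approach will be used to explore differences between the intervention and control groups".
- "Two independent sample t-test and chi-square tests will be used to determine bivariate differences". It does not say which groups are compared. A sentence on reporting by gender stands between this and the previous item.
- "Mixed effects regression models will be used to estimate the effect size of the intervention on SCA outcomes", with covariates. Neither a random effect for site nor a degrees-of-freedom method is named.
- "We will account for the clustering by study site by calculating the intraclass correlation". This closes the paragraph and is its only statement on clustering.

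**The concern.** Families at one clinic share staff, local resources and case mix, so their outcomes are likely to be correlated. A two-sample t-test or chi-square test takes its standard error from variation between families, as if each had been randomised separately. With any positive ICC that standard error is too small for an arm comparison, so p-values are too small and intervals too narrow.

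The clustering sentence does not repair this. An ICC is a descriptive quantity. It affects inference only if it enters a design-effect correction, a variance model or a site-level analysis, and none of these is described.

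At stake are the exploratory arm comparisons over the long Aim 2 list: referrals, resource enrolment, visit and medication adherence, health outcomes, quality of life and utilisation. The study exists to inform a larger cluster trial, and over-precise pilot results could mislead those who plan it.

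**Working it through.** **Inputs.** From the protocol: 2 sites per arm, m = 35 per site (70 per arm, 140 in all), ICC at most 0.01, 5% error rate, and expected proportions with an emergency department (ED) visit of 40% (intervention) and 80% (control). Assumed: two-sided tests, no dropout, equal site sizes. ICCs other than 0.01 are assumptions made to show a range.

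**The plan's own figures.** The protocol gives no type I error or interval width to reproduce. Its power claims are more than 90% for a 25-point ED difference and 90% for a 20-point adherence difference. With a two-sided pooled normal approximation, 80% vs 55% gives 89.3% power ignoring clustering and 78.7% with the design effect at ICC 0.01. For 10% vs 30% the figures are 84.9% and 73.1%. That mismatch is a separate matter, and nothing below depends on it.

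**Step 1: design effect.** DE = 1 + (m − 1) × ICC = 1 + 34 × 0.01 = 1.34. Effective sample size is 140/1.34 = 104. The correct standard error is √1.34 = 1.158 times the unadjusted one.

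**Step 2: true size of a nominal 5% test.** 2 × [1 − Φ(1.96/√DE)] = 2 × [1 − Φ(1.693)] = 0.090. The corresponding 95% interval covers about 91%.

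**Step 3: simulation under no effect.** There were 40,000 trials of 4 × 35 at each ICC. The t-test, mixed-model and site-mean columns use a normal outcome; the chi-square column uses a beta-binomial outcome with mean 0.8. Rejection rates are at the nominal 5% level.

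| ICC | DE | Formula | t-test | Chi-square | Random site intercept, Wald z | Site means, 2 df | Site variance estimated ≤ 0 |
|---|---|---|---|---|---|---|---|
| 0.005 | 1.17 | 7.0% | 7.1% | 6.9% | 5.2% | 5.0% | 57% |
| **0.01** | **1.34** | **9.0%** | **9.1%** | **9.2%** | **6.3%** | **5.1%** | **52–53%** |
| 0.02 | 1.68 | 13.0% | 13.3% | 13.2% | 8.3% | 5.0% | 44% |
| 0.05 | 2.70 | 23.3% | 24.0% | 23.6% | 12.4% | 5.0% | 29% |

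For the beta-binomial outcome, site means on 2 df rejected in 4.7% to 4.9%.

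**Step 4: interval width.** Four sites in two arms leave 4 − 2 = 2 df, with critical value 4.303. At ICC 0.01 and the true standard error, the width ratio is (4.303/1.96) × √1.34 = 2.195 × 1.158 = 2.54. With the standard error estimated from the sites, the simulated mean ratio is 2.23.

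**Step 5: on the ED outcome.** For 40% vs 80%, the unadjusted half-width is 1.96 × √[(0.24 + 0.16)/70] = 0.148. The simulated mean is 0.147, with 90% coverage. On 2 df the simulated mean is 0.334, with 95% coverage. That is about ±33 points against ±15.

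**Step 6: on a p-value.** An unadjusted p of 0.05 (z = 1.96) becomes z = 1.693 after the design effect. That gives p = 0.09 against the normal distribution and p = 0.23 against t on 2 df.

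**The case against.** The other side has five fair points.

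- **The target of the tests is inferred.** The plan does not say that the t-tests and chi-square tests compare the arms. This stands, and the concern is limited to that use. The arm comparison is introduced two sentences earlier, so it is the natural reading; if another was meant, the text needs to say so.
- **Mixed models are planned for the effect size.** In a four-site trial a site random effect is the obvious guess, and the ICC sentence may be loose wording for it. With that model and Wald z, type I error at ICC 0.01 is 6.3%, close to nominal. This stands in part: the model is not specified, the figure rises to 12.4% at an assumed ICC of 0.05, and the model does nothing for the separate t-tests and chi-square tests.
- **No intervals for arm differences are promised.** True. The interval figures show what would happen if they were reported; the p-value problem does not depend on them.
- **The factor of 2.5 mixes two causes.** True. Ignoring the ICC contributes 1.16, and moving from the normal distribution to 2 df contributes 2.2. Both follow from randomising four sites, but only the first comes from treating families as independent.
- **This is a pilot and efficacy is disclaimed.** This limits the consequence. It does not make a test valid whose p-value will be reported.

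Also, 9% applies at the protocol's ceiling, and the inflation vanishes at an ICC of zero. Against that, Preliminary Studies says earlier work on this intervention was in primary care, among children without complex conditions, so the ICC in hematology clinics is not known.

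**Conclusion.** The concern holds, and the plan is wrong as written for arm comparisons: it names tests that ignore the unit of randomisation and describes as an adjustment something that adjusts nothing. At the protocol's ICC ceiling, type I error is about 9% instead of 5%, and unadjusted 95% intervals cover about 91%. This rests on two-sided tests, 35 families at each site, no dropout, and the reading that the tests compare arms. The direction is the same for any positive ICC; the size above 0.01 depends on assumed values. No confirmatory conclusion is affected, because the protocol draws none. It should be corrected before analysis, but it does not threaten the study.

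**What to change.** Change the Aim 2 analysis text as follows.

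1. Replace the t-tests and chi-square tests for arm comparisons with one of two methods. The first is a comparison of site-level summaries on 2 df. The second is the planned mixed model with a stated random site intercept and small-sample degrees of freedom (Kenward-Roger or between-within).
2. If the mixed model is chosen, state what happens when the site variance is estimated at zero, which occurs in about half of trials at ICC 0.01. Holding the variance at zero or above while using 2 df gives type I error below 0.5%, which is very conservative. If Kenward-Roger falls back to 138 df at a zero estimate (assumed; this depends on software), it is 4.7% at ICC 0.01 and 7.2% at 0.05. The site-level comparison, or a model that lets the variance estimate go negative, avoids the problem.
3. Report arm differences as estimates with intervals, without claims of significance.
4. Reword the clustering sentence: the ICC is a reported estimate, pooled within arm over all four sites, with its 95% confidence interval. It is not the adjustment.
5. Say which groups any remaining t-tests or chi-square tests compare.

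The cost is plan wording and a few lines of code; design and data collection do not change. Intervals will be wider and unstable. For 40% vs 80% at ICC 0.01, the 2-df half-width runs from about 12 to 57 points (10th to 90th percentile), and power on 2 df is about 66% (36% for 80% vs 55%). Simple site-level summaries also drop the planned covariate adjustment, so the mixed model is the route if that is to be kept. The ICC interval from four sites will be very wide, which planners of the larger trial should see.
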